7.1.3.3 Pharmacokinetic/Pharmacodynamic Evaluations

To evaluate the immunogenicity and exposure of pembrolizumab in this indication, sample collections for analysis of anti-pembrolizumab antibodies (ADA) and PK are currently planned as shown in the Trial Flowchart. Blood samples collected for PK and ADA may only be stored at this time. Further analysis may be performed, if required. If ongoing PK and/or ADA sampling is deemed to be unnecessary by the Sponsor, it may be reduced or discontinued.

7.1.3.3.1 Blood Collection for Serum Pembrolizumab Pharmacokinetics - PK

Sample collection, storage and shipment instructions for serum PK samples will be provided in the Procedures Manual.

7.1.3.3.2 Blood Collection for Anti-Drug (Pembrolizumab) Antibodies - ADA

Sample collection, storage and shipment instructions for anti-drug antibody samples will be provided in the Procedures Manual.

7.1.3.4 Tumor Tissue Collection

A newly obtained core or excisional biopsy (fine needle aspirate not adequate) must be submitted to a central lab for characterization of PD-L1 expression as well HR, PR, and HER2 negative status. The tumor tissue must be received by the central vendor and be deemed adequate for evaluation in real time prior to subject allocation for all cohorts.

Testing for hormone receptor status will be performed with commercially validated assays that meet the following requirements:

- a) Estrogen receptor (ER) negative status is defined as <1% tumor cells positive for ER by IHC, irrespective of staining intensity
- b) Progesterone receptor (PR) negative status is defined as <1% tumor cells positive for PR by IHC, irrespective of staining intensity
- c) HER2 negative status is determined by:
 - IHC 1+, as defined by incomplete membrane staining that is faint/barely perceptible and within >10% of invasive tumor cells,
 - or**
 - IHC 0, as defined by no staining observed or membrane staining that is incomplete and is faint/barely perceptible and within \leq 10% of the invasive tumor cells,
 - or**
 - FISH negative based on:
 - Single-probe average *HER2* copy number <4.0 signals/cell, **or**
 - Dual-probe *HER2/CEP17* ratio <2.0 with an average *HER2* copy number <4.0 signals/cell

Newly-obtained specimens of tissue can be collected up to 8 weeks (56 days) prior to Day 1 provided the proper consent has been obtained. Newly obtained tumor tissue should be submitted in formalin (preferred) or as formalin-fixed paraffin embedded tumor tissue

blocks. If after agreement with the Sponsor unstained slides are submitted, the slides should be freshly cut and submitted to the testing laboratory within 14 days from site slide sectioning date otherwise a new specimen will be requested.

Additionally, if available, archived tumor tissue specimens from prior biopsies will be collected for determination of tumor PD-L1 status to compare biomarker expression in archived specimens against the in newly obtained tumor tissue that is collected as a requirement for entry into the trial. If after agreement with the Sponsor unstained slides are submitted, the slides should be freshly cut and submitted to the testing laboratory within 14 days from site slide sectioning date otherwise a new specimen will be requested.

Tumor tissue collected may also be used to support analysis of exploratory biomarkers as described in Section 4.2.3.5.

If the subject signs the Future Biomedical Research (FBR) consent, any leftover tissue that would ordinarily be discarded at the end of the main study will be retained for FBR. Details regarding time points for collection of tumor tissue are outlined in the Study Flow Chart – Section 6.1.

Detailed instructions for tissue collection, processing and shipment are provided in the Procedures Manual.

7.1.3.5 Correlative Blood Collections – Samples for Correlative, Genetic, and Circulating MDSC Analyses

Details regarding time points for blood collection to support analysis of exploratory biomarkers presented in Section 4.2.3.5 are outlined in the Study Flow Chart – Section 6.1.

Samples for planned, exploratory genetic analysis of DNA should be drawn unless there is a documented law or regulation prohibiting collection, or unless the IRB/IEC does not approve of the collection.

Blood for correlative biomarker studies should be collected prior to treatment at each specified cycle and at treatment discontinuation.

MDSCs will only be collected in the participating countries as described in the Procedures Manual.

Detailed instructions for sample collection, processing and shipment are provided in the Procedures Manual.

7.1.3.6 Future Biomedical Research

The following specimens are to be obtained as part of Future Biomedical Research:

- Leftover DNA
- Leftover tumor tissue

7.1.4 Other Procedures

7.1.4.1 Withdrawal/Discontinuation

When a subject discontinues/withdraws from participation in the trial, all applicable activities scheduled for the final trial visit should be performed at the time of discontinuation. Any adverse events which are present at the time of discontinuation/withdrawal should be followed in accordance with the safety requirements outlined in Section 7.2 - Assessing and Recording Adverse Events. Subjects who a) attain a CR or b) complete 24 months of treatment with pembrolizumab may discontinue treatment with the option of restarting treatment if they meet the criteria specified in Section 7.1.5.2.1. After discontinuing treatment following assessment of CR or 24 months of treatment, these subjects are expected to return to the site for a Safety Follow-up Visit (described in Section 7.1.5.3.2) and then proceed to the Follow-up Period of the study (described in Section 7.1.5.3.3).

7.1.4.1.1 Withdrawal From Future Biomedical Research

Subjects may withdraw their consent for Future Biomedical Research and have their specimens and all derivatives destroyed. Subjects may withdraw consent at any time by contacting the principal investigator for the main trial. If medical records for the main trial are still available, the investigator will contact the Sponsor using the designated mailbox ([contact]), and a form will be provided by the Sponsor to obtain appropriate information to complete specimen withdrawal. Subsequently, the subject's specimens will be removed from the biorepository and be destroyed. A letter will be sent from the Sponsor to the investigator confirming the destruction. It is the responsibility of the investigator to inform the subject of completion of destruction. Any analyses in progress at the time of request for destruction or already performed prior to the request being received by the Sponsor will continue to be used as part of the overall research trial data and results. No new analyses would be generated after the request is received.

In the event that the medical records for the main trial are no longer available (e.g., if the investigator is no longer required by regulatory authorities to retain the main trial records) or the specimens have been completely anonymized, there will no longer be a link between the subject's personal information and their specimens. In this situation, the request for specimen destruction cannot be processed.

7.1.4.2 Blinding/Unblinding

This is an open label trial; there is no blinding for this trial.

7.1.4.3 Calibration of Critical Equipment

The investigator or qualified designee has the responsibility to ensure that any critical device or instrument used for a clinical evaluation/test during a clinical trial that provides important information about inclusion/exclusion criteria and/or safety or efficacy parameters shall be suitably calibrated and maintained to ensure that the data obtained is reliable and/or reproducible. Documentation of equipment calibration must be retained as source documentation at the trial site.

Critical Equipment for this trial includes:

- Laboratory equipment – as required for satisfaction of entry criteria and trial assessments and routine safety evaluation of subjects
- Imaging equipment – as required for study objectives
- Drug administration equipment – as required for storage, preparation and administration (infusion) of pembrolizumab

See protocol-specified guidance in the Administrative Binder, Procedures Manual, Pharmacy Manual and Site Imaging Manual.

7.1.5 Visit Requirements

Visit requirements are outlined in Section 6.0 - Trial Flow Chart. Specific procedure-related details are provided above in Section 7.1 - Trial Procedures.

7.1.5.1 Screening

Written consent for the main study must be obtained prior to performing any protocol specific procedure including the mandatory newly obtained (fresh) tumor biopsy that is required for eligibility. Potential subjects will be evaluated to determine that they fulfill the entry requirements as set forth in Section 5.1. Visit requirements are outlined in Section 6.0 – Trial Flow Chart. Results of a test performed prior to the subject signing consent as part of routine clinical management are acceptable in lieu of a screening test if performed within the specified time frame.

Screening procedures are to be completed within 28 days prior to the first dose trial treatment except for the following:

- Laboratory tests and evaluation of ECOG status are to be performed within 10 days prior to the first dose of trial treatment.
- For women of reproductive potential, a urine pregnancy test will be performed within 72 hours prior to the first dose of trial treatment. If urine pregnancy results cannot be confirmed as negative, a serum pregnancy test will be required (performed by the local study site laboratory).

- Initial tumor imaging must be performed within 28 days prior to the date of allocation.
- A “newly obtained” tumor biopsy sample may be obtained within approximately 56 days of the first dose of trial treatment. See Section 7.1.3.4 for additional details regarding tumor tissue requirements.

Screening procedures may be repeated after consultation with the Sponsor. Subjects may be rescreened after initially failing to meet the inclusion/exclusion criteria. Results from assessments performed during the initial screening period are acceptable in lieu of a repeat screening test if performed within the specified time frame and the inclusion/exclusion criteria is met.

7.1.5.2 Treatment Cycles

Visit requirements are outlined in Section 6.0 – Trial Flow Chart. Specific procedure-related details are provided above in Section 7.1 – Trial Procedures.

7.1.5.2.1 Second Course Phase (Retreatment Period)

Subjects who stop pembrolizumab with SD or better may be eligible for up to an additional 17 cycles (approximately one year) of pembrolizumab therapy if they progress after stopping study treatment. This retreatment is termed the Second Course Phase of this study and is only available if the study remains open and the subject meets the following conditions:

- **Either**
 - Stopped initial treatment with pembrolizumab after attaining an investigator-determined confirmed CR according to RECIST 1.1, and
 - Was treated for at least 8 cycles (24 weeks) with pembrolizumab before discontinuing therapy
 - Received at least two treatments with pembrolizumab beyond the date when the initial CR was declared

OR

- Had SD, PR or CR and stopped pembrolizumab treatment after 35 administrations (approximately 24 months) of study therapy for reasons other than disease progression or intolerability

AND

- Experienced an investigator-determined confirmed radiographic disease progression after stopping their initial treatment with pembrolizumab
- Did not receive any anti-cancer treatment since the last dose of pembrolizumab

- Has a performance status of 0 or 1 on the ECOG Performance Scale
- Demonstrates adequate organ function as detailed in Section 5.1.2
- Female subject of childbearing potential should have a negative serum or urine pregnancy test within 72 hours prior to receiving retreatment with study medication.
- Female subject of childbearing potential should be willing to use 2 methods of birth control or be surgically sterile, or abstain from heterosexual activity for the course of the study through 120 days after the last dose of study medication (Reference Section 5.7.2). Subjects of child bearing potential are those who have not been surgically sterilized or have been free from menses for > 1 year.
- Does not have a history or current evidence of any condition, therapy, or laboratory abnormality that might interfere with the subject's participation for the full duration of the trial or is not in the best interest of the subject to participate, in the opinion of the treating investigator.
- The subject meets the safety parameters listed in the inclusion/exclusion criteria.
- The trial is ongoing.

Subjects who restart treatment will be retreated at the same dose and dose interval as when they last received pembrolizumab. Treatment will be administered for up to one additional year.

An objective response or disease progression that occurs during the Second Course Phase for a subject will not be counted as an event for the primary analysis of either endpoint in this trial.

Visit requirements are outlined in Section 6.0 – Trial Flow Chart.

7.1.5.3 Post-Treatment

7.1.5.3.1 Discontinuation Visit

The Discontinuation Visit should occur at the time study treatment is discontinued for any reason. If the Discontinuation Visit occurs 30 days from the last dose of study treatment, at the time of the mandatory Safety Follow up Visit, procedures do not need to be repeated. Visit requirements are outlined in Section 6.0 – Trial Flow Chart. Specific procedure-related details are provided above in Section 7.1 – Trial Procedures. Additional details regarding subject withdrawal and discontinuation are presented in Section 5.8.

7.1.5.3.2 Safety Follow-up Visit

The mandatory Safety Follow-Up Visit should be conducted approximately 30 days after the last dose of trial treatment or before the initiation of a new anti-cancer treatment, whichever comes first. All AEs that occur prior to the Safety Follow-Up Visit should be recorded.

Subjects with an AE of Grade > 1 will be followed until the resolution of the AE to Grade 0-1 or until the beginning of a new anti-cancer therapy, whichever occurs first. SAEs that occur within 90 days of the end of treatment or before initiation of a new anti-cancer treatment should also be followed and recorded regardless of causality. Beyond 90 days, only SAE and ECIs that are considered related to trial treatment should be reported.

Subjects who are eligible for retreatment with pembrolizumab (as described in Section 7.1.5.2.1) may have up to two safety follow-up visits, one after the Treatment Period and one after the Second Course Phase.

7.1.5.3.3 Follow-up Visits

Subjects who discontinue trial treatment for a reason other than disease progression will move into the Follow-Up Phase and should be assessed every 9 weeks (63 ± 7 days) in the first year and every 12 weeks (84 ± 7 days) after year 1 by tumor imaging to monitor disease status. The Sponsor may request survival status to be assessed at additional time points during the course of the study (not to exceed approximately 12 weeks). Every effort should be made to collect information regarding disease status until the start of new anti-cancer therapy, disease progression, death, end of study or if the subject begins retreatment with pembrolizumab as detailed in Section 7.1.5.2.1. Information regarding post-study anti-cancer treatment will be collected if new treatment is initiated.

Subjects who are eligible to receive retreatment with pembrolizumab according to the criteria in Section 7.1.5.2.1 will move from the Follow-Up Phase to the Second Course Phase when they experience disease progression. Details are provided in Section 6.2 – Trial Flow Chart for Retreatment with pembrolizumab.

7.1.5.3.4 Survival Follow-up

Once a subject experiences confirmed disease progression or starts a new anti-cancer therapy, the subject moves into the Survival Follow-Up Phase and should be contacted by telephone approximately every 12 weeks to assess for survival status until death, withdrawal of consent, or the end of the study, whichever occurs first.

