5.2.1.2 Dose Modification (Escalation/Titration/Other)

Pembrolizumab dose reductions are not applicable to this study. However, pembrolizumab must be withheld for drug-related toxicities and severe or life-threatening AEs as described in [Table 4](#) below. If a dose must be held/delayed do not complete a cycle visit until the subject is dosed again. When pembrolizumab is restarted, this dose would be considered Day 1 of the missed cycle.

Adverse events (both non-serious and serious) associated with pembrolizumab exposure may represent an immunologic etiology. These immune-related adverse events (irAEs) may occur shortly after the first dose or several months after the last dose of treatment and may affect more than one body system simultaneously. Therefore, early recognition and initiation of treatment is critical to reduce complications. Based on existing clinical trial data, most irAEs were reversible and could be managed with interruptions of pembrolizumab, administration of corticosteroids and/or other supportive care. For suspected irAEs, ensure adequate evaluation to confirm etiology or exclude other causes. Additional procedures or tests such as bronchoscopy, endoscopy, skin biopsy may be included as part of the evaluation. Based on the severity of irAEs, withhold or permanently discontinue pembrolizumab and administer corticosteroids. Dose modification and toxicity management guidelines for irAEs associated with pembrolizumab are provided in [Table 4](#). See Section 5.6 for supportive care guidelines, including use of corticosteroids.

Table 4 Dose Modification and Toxicity Management Guidelines for Immune-related AEs Associated with Pembrolizumab

General instructions:				

 1. Corticosteroid taper should be initiated upon AE improving to Grade 1 or less and continue to taper over at least 4 weeks. 2. For situations where pembrolizumab has been withheld, pembrolizumab can be resumed after AE has been reduced to Grade 1 or 0 and corticosteroid has been tapered. Pembrolizumab should be permanently discontinued if AE does not resolve within 12 weeks of last dose or corticosteroids cannot be reduced to ≤ 10 mg prednisone or equivalent per day within 12 weeks. 3. For severe and life-threatening irAEs, IV corticosteroid should be initiated first followed by oral steroid. Other immunosuppressive treatment should be initiated if irAEs cannot be controlled by corticosteroids. 				

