6.0 TRIAL FLOW CHART

6.1 Initial Treatment Phase

Trial Period:		Screening Phase		Treatment Cycles ^a						End of Treatment	Post-Treatment		
				1	2	3	4	To be repeated beyond 6 cycles			Discon	Safety Follow-up	Follow Up Visits ^b
5	6												
Treatment Cycle/Title:		Screening (Visit 1)											
Scheduling Window (Days) ^d :	-56 to -1	-28 to -1	-10 to -1	± 3 ^d	± 3	± 3	± 3	± 3	± 3	At time of discon	30 days post discon (± 3 days)	Every 9 weeks post discon (± 7 days)	Every 12 weeks (± 7 days)
Administrative Procedures													
Informed Consent	X ^e												
Informed Consent for Future Biomedical Research		X ^f											
Inclusion/Exclusion Criteria		X											
Subject Identification Card		X											
Demographics and Medical History		X											
Prior and Concomitant Medication Review ^g		X		X	X	X	X	X	X	X	X		
Clinical Procedures/Assessments													
Review Adverse Events ^h	X	X	X	X	X	X	X	X	X	X	X ⁱ	X ⁱ	
12-Lead Electrocardiogram [(ECG) (Local)]		X											
Full Physical Examination		X								X			
Directed Physical Examination				X	X	X	X	X	X				
Vital Signs, Weight and Height ^j		X		X	X	X	X	X	X	X			
ECOG Performance Status			X	X	X	X	X	X	X	X			
Obtain randomization number and study drug information using IVRS/IWRS				X ^k									
Pembrolizumab Administration ^k				X ^k	X	X	X	X	X				
Post-study Anticancer Therapy Status												X	X
Survival Status ^c				----->									X
Laboratory Procedures/Assessments: Analysis performed by LOCAL													

Trial Period: Treatment Cycle/Title:		Screening Phase	Treatment Cycles ^a							End of Treatment	Post-Treatment		
		Screening (Visit 1)	1	2	3	4	To be repeated beyond 6 cycles		Discon	Safety Follow-up	Follow Up Visits ^b	Survival Follow-up ^c	
							5	6					
Scheduling Window (Days) ^d :	-56 to -1	-28 to -1	-10 to -1	± 3 ^d	± 3	± 3	± 3	± 3	± 3	At time of discon	30 days post discon (± 3 days)	Every 9 weeks post discon (± 7 days)	Every 12 weeks (± 7 days)
laboratory													
Pregnancy Test – Serum or Urine ^l			X										
Blood for menopausal status (if applicable) ^m			X										
PT/INR and aPTT ⁿ			X ^o										
CBC with Differential ^p			X ^o	X	X	X	X	X ^q	X	X	X ^r		
Chemistry Panel ^p			X ^o	X	X	X	X	X ^q	X	X	X ^r		
Urinalysis			X ^o										
T3, FT4 and TSH ^q			X ^o	X		X		X ^q			X ^r		
Laboratory Procedures/Assessments: Analysis performed by CENTRAL laboratory													
Blood for Pharmacokinetics ^{s,t}				X ^s	X ^s			X ^s			X ^s	X ^s	

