- e. Written informed consent must be obtained prior to performing any protocol specified procedure. Please note that the window for acquiring the “newly obtained” tissue specimen is within 56 days of the first dose of study drug and written consent should be obtained prior to acquiring the specimen if a biopsy for the study is performed. Results of a test performed prior to the subject signing consent as part of routine clinical management are acceptable in lieu of a screening test if performed within the window specified for screening procedures (e.g., within 28 days prior to the first dose of trial treatment for required lab tests). Screening number will be assigned when the study informed consent is signed.
- f. Signing the informed consent for future biomedical research (FBR) sample is optional. Detailed instructions for the collection and management of specimens for FBR are provided in the Procedures Manual and Section 12.2.
- g. Prior medications – Record all medications taken within 28 days of screening visit. Concomitant medications – Enter new medications started during the trial through the Safety Follow-up visit. Record all medications taken for SAEs as defined in Section 7.2
- h. AEs and laboratory safety measurements will be graded per NCI CTCAE version 4.0. All AEs, whether gradable by CTCAE or not, will also be evaluated for seriousness.
- i. Record all AEs occurring within 30 days after the last dose of trial treatment. Report all SAEs (related and unrelated to trial treatment) and ECIs occurring up until 90 days after the end of treatment or 30 days after the end of treatment if the subject initiates new anticancer therapy, whichever is earlier. Afterwards, report only SAEs and ECIs that are related to trial treatment.
- j. Vital signs to include temperature, pulse, respiratory rate, weight and blood pressure. Height will be measured at screening visit only. Vital signs will be collected at screening, prior to the administration of each dose of trial treatment at every cycle and at treatment discontinuation.
- k. Study personnel will access IVRS/IWRS to obtain randomization number and study drug assignment. Pembrolizumab is given as a 200 mg dose on the first day of each 3 week cycle. Cycle 1 treatment must be given within 3 days of randomization number assignment in IVRS/IWRS.

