7.1.1.5.2 Concomitant Medications

The investigator or qualified designee will record medication, if any, taken by the subject during the trial. All medications related to reportable SAEs and ECIs should be recorded as defined in Section 7.2.

7.1.1.5.2.1 Subsequent Anti-cancer Therapy Status

The investigator or qualified designee will review all new anti-cancer therapy initiated after the last dose of trial treatment. If a subject initiates a new anti-cancer therapy within 30 days after the last dose of trial treatment, the 30 day Safety Follow-up visit must occur before the first dose of the new therapy. Once new anti-cancer therapy has been initiated the subject will move into survival follow-up.

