7.1.2 Clinical Procedures/Assessments

7.1.2.1 Adverse Event (AE) Monitoring

The investigator or qualified designee will assess each subject to evaluate for potential new or worsening AEs as specified in the Trial Flow Chart and more frequently if clinically indicated. Adverse events will be graded and recorded throughout the study and during the follow-up period according to NCI CTCAE Version 4.0 (see Appendix 12.7). Toxicities will be characterized in terms regarding seriousness, causality, toxicity grading, and action taken with regard to trial treatment.

For subjects receiving treatment with pembrolizumab all AEs of unknown etiology associated with pembrolizumab exposure should be evaluated to determine if it is possibly an event of clinical interest (ECI) of a potentially immunologic etiology (termed immune-related adverse events, or irAEs); see the separate ECI guidance document in the administrative binder regarding the identification, evaluation and management of potential irAEs.

Please refer to Section 7.2 for detailed information regarding the assessment and recording of AEs.

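### After the day-30 safety visit, subjects who stopped for progression and are not on new therapy have no scheduled adverse event review, although SAEs and ECIs are reportable to day 90

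*Combined protocol and SAP*

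**What the plan says.** **Collection window.** Footnote i of flow chart 6.1 reads: "Report all SAEs (related and unrelated to trial treatment) and ECIs occurring up until 90 days after the end of treatment". Sections 7.2.3.1 and 7.2.3.2 set the same 90 days, shortened if new anticancer therapy is started, and require reporting within 24 hours. After the window, only treatment-related events are reportable.

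**Reason for a long window.** Section 5.2.1.2 says that immune-related events "may occur shortly after the first dose or several months after the last dose of treatment".

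**Where events are looked for.** Section 7.1.2.1 has the investigator assess subjects for adverse events "as specified in the Trial Flow Chart and more frequently if clinically indicated". In flow charts 6.1 and 6.2 the row "Review Adverse Events" is marked at every treatment cycle, at Discontinuation, at Safety Follow-up and at Follow Up Visits. It is blank under Survival Follow-up. The 90-day footnote (i in 6.1, g in 6.2) hangs only on the Safety Follow-up and Follow Up Visits marks.

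**Who attends which contact.**
- All subjects: "The mandatory Safety Follow-Up Visit should be conducted approximately 30 days after the last dose of trial treatment" (7.1.5.3.2). If new therapy starts within 30 days of the last dose, "the 30 day Safety Follow-up visit must occur before the first dose of the new therapy" (7.1.1.5.2.1).
- Subjects who stopped without progression: "Subjects who discontinue trial treatment for a reason other than disease progression will move into the Follow-Up Phase" (7.1.5.3.3), with visits every 9 weeks in the first year.
- Subjects with confirmed progression or on new therapy: "the subject moves into the Survival Follow-Up Phase and should be contacted by telephone approximately every 12 weeks to assess for survival status" (7.1.5.3.4).

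**The concern.** A 90-day reporting rule finds events only if someone asks about them. For subjects without progression the schedule asks again inside the window. For subjects with progression it does not, and a site following the chart would have no prompt to ask during a survival call. After day 30, events in that group are recorded only if the site happens to learn of them.

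Safety and tolerability across Cohorts A to C is a primary objective (3.1, objective 3), to be described by PD-L1 status within line of treatment. Late immune-related events are a risk the protocol itself names, and there is no data monitoring committee (7.3.1). If ascertainment depends on whether the subject progressed, and the share progressing differs between PD-L1 groups or lines of treatment, the late SAE and ECI rates in those groups are not measured with equal intensity.

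**Working it through.** The plan states no figure on this point, so the check sets the visit schedule against the collection window. Day 0 is the end of treatment, with the last dose and discontinuation taken as the same day; any lag between them moves visits counted from discontinuation later by that lag.

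**Inputs**
- Window: day 90 if no new therapy is started (7.2.3.1, 7.2.3.2, footnote i).
- Safety Follow-up: day 30 ± 3 (6.1).
- Follow Up Visits: every 63 ± 7 days after discontinuation (6.1, 7.1.5.3.3).
- Survival calls: about every 84 ± 7 days (6.1); the start point is not stated.

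**Days at issue.** Day 31 to day 90 is 90 − 30 = 60 days, and 60/90 = 67% of the window.

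**Scheduled contacts, subject not on new therapy**

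| | Stopped without progression | Stopped for confirmed progression |
|---|---|---|
| Discontinuation | review | review |
| Day 27–33 | review | review |
| Day 31–90, after the safety visit | Follow-up Visit, 63 ± 7 = day 56–70, review | survival call only, no review |
| Reviews after the safety visit, to day 90 | 1 | 0 |

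**Position of the first call.** Counted from discontinuation: 84 ± 7 = day 77–91. Counted from the safety visit: 30 + 84 = 114, ± 7 = day 107–121. In the first case most possible dates fall before the window closes; in the second all fall after it. Neither call carries an adverse event mark.

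**Effect of new therapy.** The documents end the window in three ways. As an illustration, take a subject who starts new therapy on day 50:
- 7.2.3.1, the main text of 7.2.3.2, 5.8 and footnote i: 30 days after treatment ended, so day 30.
- Trial Summary, 2.1 and 7.1.5.3.2: when new therapy starts, so day 50 (the first two add a minimum of 30 days).
- 7.2.3.2, item 3, for ECIs: 30 days after new therapy starts, so 50 + 30 = day 80.

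Under the rule in 7.2.3.1 this subject has no uncovered days. Under the rule in 2.1 there are 50 − 30 = 20, and under item 3 of 7.2.3.2 there are 80 − 30 = 50. The size of the affected group therefore depends on which rule governs.

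**Can a loss be computed?** Only from assumptions. Suppose 60–85% of about 285 subjects stop for progression (171–242), half of them are not on new therapy by day 90 (86–121), 2–10% of those have a reportable event in days 31–90, and 10–50% of such events are missed. The loss is then 86 × 0.02 × 0.10 = 0.2 to 121 × 0.10 × 0.50 = 6 events. Only the 285 comes from the documents, so this range is an illustration and not a finding.

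**The case against.** The strongest reply is that the duty to collect is complete. SAEs and ECIs must be reported within 24 hours to day 90 whatever their cause, with no exemption for progressors. Section 7.1.5.3.2 says SAEs in that period are to be followed and recorded. Section 7.1.2.1 also speaks of recording events during the follow-up period. This stands: the obligation is not missing. But a duty to report does not find an event, and the ECI assessment described in 7.2.3.2 is tied to dosing, which has ended.

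Footnote s of 6.1 lists a PK and antibody sample 3 months after discontinuation unless new therapy has begun. As worded it is not limited to subjects without progression, so it may give a contact near day 90. It is charted under Follow Up Visits, is not an adverse event review, and may be reduced or dropped under 7.1.3.3.

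The survival calls are not purely about survival: both charts also mark post-study anticancer therapy under them, and they pick up deaths. That is correct. It also shows that the call can carry another question.

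The affected group is narrower than all progressors, because early new therapy shortens the window. Progression itself is not an adverse event (7.2) and is exempt from SAE reporting (7.2.3.3). The trial is for estimation, with no treatment comparison to bias. All of this stands and limits the consequence.

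A reader might infer that progressors go straight to telephone calls with no safety review after treatment. The documents do not support that: review is marked at Discontinuation and at the day-30 visit, which is mandatory and must come before any new therapy started within 30 days. A reader might also infer that a 12-week call interval is bound to fall short of day 90. With no start point stated, that cannot be established.

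**Conclusion.** The point holds in a limited form. For subjects who stopped for confirmed progression and have not started new anticancer therapy, the plan schedules no adverse event review between the day-30 visit and day 90, while subjects who stopped for other reasons have one at about day 56 to 70. This follows from the two flow charts with 7.1.5.3.3 and 7.1.5.3.4; it rests on reading the chart as the assessment schedule, as 7.1.2.1 does.

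It is a gap in scheduled ascertainment covering 60 of 90 days, not in the reporting obligation. It would be tempting to state that late SAEs and ECIs are under-counted by some number. The documents do not support that: they give neither the share of progressors without new therapy, nor the late event rate, nor the share missed without a prompt. What can be said is that ascertainment becomes passive for one group, that the group is defined by efficacy outcome, and that this touches a primary objective. It merits a cheap improvement; it does not undermine the safety analysis as a whole.

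**What to change.** 1. In flow charts 6.1 and 6.2, mark "Review Adverse Events" under Survival Follow-up, limited by footnote to SAEs and ECIs.
2. Add a matching sentence to 7.1.5.3.4.
3. State the start point of the calls, and time one existing call at or just after day 90 from the last dose. On it, ask about SAEs and ECIs since the Safety Follow-up Visit.
4. In the same edit, reconcile how new anticancer therapy ends the window: the Trial Summary, 2.1 and 7.1.5.3.2, against 5.8, 7.2.3.1, the main text of 7.2.3.2 and the flow-chart footnotes, against item 3 of 7.2.3.2.

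No visit is added and no treatment rule changes. The cost is a few minutes on a call that is already made, and probably a slightly higher reported count of SAEs and ECIs.
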